15.4.2. Clinical Laboratory Evaluations

Laboratory parameters will be summarized in standard international (SI) system of units by treatment group using descriptive statistics at Baseline and at each on-study evaluation. Re-test or unscheduled results will not be summarized but will be included in the data listings. The change from Baseline will also be summarized. Baseline is defined as the mean of all available evaluations prior to treatment.

In addition, shift tables (ie, low-normal-high at Baseline versus low-normal-high at post Baseline visit in a 3-by-3 contingency table) from Baseline to worst value, last value, and at each scheduled post-Baseline visit will be provided for hematology and serum chemistry by treatment group to assess changes in laboratory values from Baseline to each on-study evaluation.

15.4.3. Additional Safety Analysis

Vital Signs and Weight

The results and change from Baseline to each on-study evaluation visit will be summarized by treatment group for weight, oral temperature, sitting heart rate, respiratory rate and sitting blood pressure.

Electrocardiograms

Electrocardiogram (ECG) results will be summarized at each on-study visit descriptively, including the number and percentage of patients with normal, abnormal not clinically significant, and abnormal clinically significant results at Baseline and each on-study evaluation.

15.4.4. Adverse Events of Special Interest

Pruritus: Treatment-emergent pruritus, defined as any PT including “Prur,” will be summarized separately by the MedDRA SOC, treatment group, and PT as a subset of all TEAEs. This summary will be repeated for patients with “new or worsened” pruritus events, as defined as follows:

- Mild, moderate, or severe treatment-emergent pruritus events in patients with no pruritus at Baseline, or
- Worsening of the severity of the Baseline condition in patients with pruritus at Baseline.

Baseline pruritus is defined as the Investigator’s rating of severity as collected on the PBC Disease History eCRF. Patients whose Baseline severity is severe will be counted as worsening if an AE of pruritus with severe is recorded.

An analysis of treatment-emergent pruritus event days per patient years on study will be performed. The days at each severity grade, including the total days of event, the total patient years on study, and the event days per patient year on study at each severity grade, including the total, will be summarized. Each individual patient year on study will be derived as the last known date during the study minus the first dose date plus 1 divided by 365.25 days/year.

In order to explore the relationship between pruritus and the investigational product, the following time-to-event analyses will be performed:

- Time to first onset of treatment-emergent pruritus
 - The time to the start of the first episode will be calculated by date of onset of first episode – date of first dose of investigational product + 1.
 - Patients who never reported an AE of pruritus will be censored at the date of last contact.
- Time to onset of the first moderate or severe treatment-emergent pruritus
 - The time to the start of the first moderate or severe pruritus will be calculated by date of onset of the first moderate or severe pruritus – date of first dose of investigational product +1.

- Patients who never reported a moderate or severe AE of pruritus will be censored at the date of completion or discontinuation.
- Time to onset of the first severe treatment-emergent pruritus
 - The time to the start of the first severe pruritus will be calculated by date of onset of the first severe pruritus – date of first dose of investigational product +1.
 - Patients who never reported a severe AE of pruritus will be censored at the date of completion or discontinuation.

The analysis of time to first onset of treatment-emergent pruritus AE, time to onset of the first moderate or severe treatment-emergent pruritus, and onset of the first severe treatment-emergent pruritus will include the number of patients with pruritus (first onset, first moderate or severe, first severe), the number of patients without pruritus (censored), and the minimum and maximum times in days. KM estimates will be calculated by treatment group. The tabulation will include the KM estimate methodology using 25th, 50th (median), and 75th percentiles of the medians and corresponding with associated 2-sided 95% confidence intervals (CIs), if the medians can be estimated as well as percentage of censored observations.

Fatigue: Treatment-emergent fatigue is defined as any PT which includes “Fatigue.” New or worsened treatment-emergent fatigue is defined as follows:

- Any mild, moderate, or severe treatment-emergent fatigue events in patients with no fatigue at Baseline, or
- Worsening of the severity of the Baseline condition in patients with fatigue at Baseline.

Baseline fatigue is defined as the Investigator’s rating of severity as collected on the PBC Disease History eCRF. Patients whose Baseline severity is severe will be counted as worsening if an AE of fatigue with severe is recorded.

An analysis of treatment-emergent fatigue event days per patient years on study will be performed. The days at each severity grade, including the total days of event, the total patient years on study, and the event days per patient year on study at each severity grade, including the total, will be summarized. Each individual patient year on study will be derived as the last known date during the study minus the first dose date plus 1 divided by 365.25 days/year.

In order to explore the relationship between fatigue and the investigational product, the following time-to-event analyses will be performed:

- Time to first onset of treatment-emergent fatigue
 - The time to the start of the first episode will be calculated by date of onset of first episode – date of first dose of investigational product + 1.
 - Patients who never reported an AE of fatigue will be censored at the date of last contact.
- Time to onset of the first moderate or severe treatment-emergent fatigue

- The time to the start of the first moderate or severe fatigue will be calculated by date of onset of the first moderate or severe fatigue – date of first dose of investigational product +1.
- Patients who never reported a moderate or severe AE of fatigue will be censored at the date of last contact.
- Time to onset of the first severe treatment-emergent fatigue
 - The time to the start of the first severe fatigue will be calculated by date of onset of the first severe fatigue – date of first dose of investigational product +1.
 - Patients who never reported a severe AE of fatigue will be censored at the data of last contact.

The analysis of time to first onset of treatment-emergent fatigue AE, time to onset of the first moderate or severe treatment-emergent fatigue, and onset of the first severe treatment-emergent fatigue will include the number of patients with pruritus (first onset, first moderate or severe, first severe), the number of patients without fatigue (censored), and the minimum and maximum times in days. KM estimates will be calculated by treatment group. The quartiles, including the median time-to-event and their respective 2-sided 95% CIs, will be presented. KM estimates will be plotted as a “survival curve” for each treatment group.

15.5. Efficacy Analyses

This study does not plan to test a formal hypothesis for any efficacy endpoint.

The endpoints of efficacy assessments are change in total and direct bilirubin, INR, creatinine, albumin, platelets, ALP, ALT, AST, and GGT from baseline to Week 48 (end of the study), change from baseline to Week 48 in CP score and components of the CP score, and change from baseline to Week 48 in MELD and components of the MELD score. Analyses of change from Baseline to Week 48 (end of study) will be modelled between treatment groups using ANCOVA model with change from Baseline as the dependent variable, treatment group and randomization stratification factor as fixed effects and the baseline value as a covariate. The same analysis will be carried out using percentage change from Baseline as the dependent variable.

Analyses of change from Baseline to Week 48 (end of study) will be modelled between treatment groups using ANCOVA model with change from Baseline as the dependent variable, treatment group and randomization stratification factor as fixed effects and the baseline value as a covariate. The same analysis will be carried out using percentage change from Baseline as the dependent variable.

Summary statistics of the laboratory values will be provided by treatment group. The results, change from Baseline, and percentage change from Baseline values, as well as estimates of least-square (LS) means, standard errors (StdErr), and 2-sided 95% CIs, will be presented by treatment group. Estimates of the mean difference between treatment groups, the StdErr of the difference, and 2-sided 95% CI of the difference will also be presented.

Risk Scores: Changes from baseline in the MELD score and in CP score, C4, FGF-19 and plasma bile acids will be summarized and analyzed using the Wilcoxon Rank Sum Test. The median differences and 95% CI of the median differences between treatment groups will be

constructed using Hodges-Lehmann estimate. If the median differences between treatments are not symmetrical around the median, the Sign Test may be used.

Shifts in MELD scores from Baseline will be reported by visit using the following categories: <10, 10 to <12, 12 to <13, 13 to <14, 14 to <15, and ≥ 15 .

CP class will be presented in shift tables showing the shift from baseline to each scheduled post-baseline visit by the count and percentage of patients within each shift classification.

Individual factors will be presented in a listing.

15.6. Additional Efficacy Analyses

Analyses of changes in liver stiffness (TE) and liver fibrosis (ELF [HA, P3NP, and TIMP-1]) will be summarized and analyzed using the same methodology specified for the key secondary analyses of change in bilirubin.

The following clinical endpoints will be captured in the study:

- Time to death (all cause)
- Time to liver-related death
- Time to liver transplant
- MELD score ≥ 15 (for patients with MELD ≤ 12 at baseline)
- Hospitalization (as defined by a stay of 24 hours or greater) for new onset or recurrence of:
 - Time to variceal bleed
 - Time to hepatic encephalopathy (as defined by a West Haven score of ≥ 2)
 - Time to spontaneous bacterial peritonitis (confirmed by diagnostic paracentesis)
- Time to uncontrolled ascites (diuretic resistant ascites requiring therapeutic paracentesis at a frequency of at least twice in a month).

The incidence and time to first occurrence of any above listed clinical events will be summarized by treatment group using the log rank test stratified by the randomization stratification factor. KM estimates of the distribution of the time-to-event will be tabulated and graphed by treatment group. The tabulation will include the KM methodology using 25th, 50th (median), and 75th percentiles with associated 2-sided 95% confidence intervals (CIs), as well as percentage of censored observations. The number and percent of patients censored and with events will be presented. The hazard ratio and 2-sided 95% CI will be estimated based on a Cox regression model stratified by randomization strata.

In addition, the incidence and time to each of the above clinical events, and the incidence and time to occurrence of hepatocellular carcinoma (HCC) will be summarized by treatment group using the same methods as defined above.

Full details regarding additional efficacy analyses will be detailed in the SAP.

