6.3. Additional Objectives

- To evaluate the effect of OCA treatment compared to placebo on:
 - Noninvasive markers of liver fibrosis (Enhanced Liver Fibrosis [ELF]TM score)
 - Noninvasive measurement of liver stiffness (transient elastography [TE])
- To assess the PK/Pharmacodynamic (PD) relationship of OCA with:
 - PK parameters compared to PD parameters and safety and tolerability assessments
- To assess patient reported outcomes (Pruritus Visual Analogue Scale [VAS], PBC-40, EQ 5D-5L, Chronic Liver Disease Questionnaire [CLDQ])

- To assess clinical events consistent with end-stage liver disease
 - Death (all cause)
 - Liver transplant
 - MELD score ≥ 15 (for patients with MELD ≤ 12 at baseline)
 - Hospitalization (as defined by a stay of 24 hours or greater) for new onset or recurrence of: variceal bleed, hepatic encephalopathy (as defined by a West Haven score of ≥ 2), spontaneous bacterial peritonitis
 - Uncontrolled ascites (diuretic resistant ascites requiring therapeutic paracentesis at a frequency of at least twice in a month)
 - Hepatocellular carcinoma (HCC)

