8.2. Patient Inclusion Criteria

1. A definite or probable diagnosis of PBC (consistent with American Association for the Study of Liver Diseases [AASLD] and European Association for the Study of the Liver [EASL] Practice Guidelines [Lindor 2009, EASL 2009]), defined as having ≥ 2 of the following 3 diagnostic factors:
 - History of elevated ALP levels for at least 6 months
 - Positive antimitochondrial antibody (AMA) titer or if AMA negative or low titer ($\leq 1:80$), PBC-specific antibodies (anti-GP210 and/or anti-SP100) and/or antibodies against the major M2 components (PDC-E2, 2-oxo-glutaric acid dehydrogenase complex)
 - Liver biopsy consistent with PBC (collected at any time prior to Screening)
2. Evidence of cirrhosis including at least one of the following:
 - Biopsy results consistent with PBC Stage 4
 - Liver stiffness as assessed by TE Value ≥ 16.9 kPa
 - Clinical evidence in the absence of acute liver failure consistent with cirrhosis including: gastroesophageal varices, ascites, radiological evidence of cirrhosis (nodular liver or enlargement of portal vein and splenomegaly)
 - Combined low platelet count ($< 140\,000/\text{mm}^3$) with:
 - persistent decrease in serum albumin, or
 - elevation in prothrombin time /INR (not due to antithrombotic agent use), or
 - elevated bilirubin ($2 \times$ ULN)
3. Satisfy the criteria of the modified CP classification for hepatic impairment during Screening:
 - Moderate: CP-B (Scores 7 to 9) or
 - Severe: CP-C (Scores 10 to 12)
4. MELD score of 6 to 24 at Screening
5. Age ≥ 18 years
6. Taking UDCA for at least 12 months (stable dose for ≥ 3 months) prior to Day 1, or unable to tolerate or unresponsive to UDCA (no UDCA for ≥ 3 months)
7. Contraception: Female patients must be postmenopausal, surgically sterile, or if premenopausal (and not surgically sterile), be prepared to use ≥ 1 effective method of contraception during the study and for 30 days after the end of treatment visit. Effective methods of contraception are considered to be those listed below:
 - Barrier method, ie, (a) condom (male or female) with spermicide **or** (b) diaphragm with spermicide; or

- Intrauterine device; or
 - Vasectomy (partner); or
 - Hormonal (eg, contraceptive pill, patch, intramuscular implant or injection); or
 - Abstinence, if in line with the preferred and usual lifestyle of the patient (where abstinence is defined as refraining from heterosexual intercourse)

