11. OVERVIEW OF ASSESSMENTS

The assessments supporting the objectives for the study are in Table 7:

Table 7: Table of Assessments

Primary Objectives	Assessments
PK parameters	OCA and its conjugates glyco-OCA and tauro-OCA, and metabolite OCA glucuronide
Safety and tolerability	SAEs and TEAEs, physical exam, ECG, vital signs, clinical laboratory assessments, discontinuations, pruritus, and fatigue
Secondary Objectives	Assessments
Changes in risk scores	Changes in MELD and in CP Scores and components of the CP score and MELD score
Changes in liver biochemistry and hepatobiliary damage	Total and direct bilirubin, ALP, ALT, AST, GGT, INR, creatinine, albumin, platelets
PD parameters	FGF-19, C4, and plasma bile acids
Additional Objectives	Assessments
Noninvasive measurements of liver fibrosis, liver stiffness and cirrhosis	TE/ELF (HA, P3NP, and TIMP-1)
PK/PD relationship	PK parameters compared to PD parameters and safety and tolerability assessments (above)
Patient-reported outcomes	Pruritus VAS, PBC-40, EQ-5D-5L, CLDQ
Clinical events	Death (all-cause and liver-related), liver transplant, MELD score ≥ 15 (for patients with MELD ≤ 12 at baseline), hospitalization for new onset or recurrence of: variceal bleed, hepatic encephalopathy, spontaneous bacterial peritonitis, uncontrolled ascites, and HCC.

ALP = alkaline phosphatase; ALT = alanine aminotransferase; AST = aspartate aminotransferase;
C4 = 7 α -hydroxy-4-cholesten-3-one; CLDQ = Chronic Liver Disease Questionnaire; CP = Child-Pugh; ECG =
electrocardiogram; ELF = enhanced liver fibrosis;
FGF-19 = fibroblast growth factor-19; GGT = gamma-glutamyl transferase; HA = hyaluronic acid;
INR = international normalized ratio; MELD = Model End Stage Liver Disease; OCA = obeticholic acid; P3NP =
procollagen 3 N-terminal peptide; PBC = Primary Biliary Cholangitis;
PD = pharmacodynamic; PK = pharmacokinetic; SAE = serious adverse event; TE = Transient Elastography;
TEAE = treatment emergent adverse events; TIMP-1 = tissue inhibitor of metalloproteinase 1; VAS = visual
analog scale

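### Sections 6.3 and 15.6 count uncontrolled ascites as an event with no new-onset or baseline condition, in conflict with Table 7, so any patient who already has it could become an early event unrelated to treatment

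*Protocol*

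**What the plan says.** Section 15.6 of the Protocol lists the clinical events, then analyses the time to the first of any of them, and the time to each separately, by stratified log rank test, Kaplan-Meier curves and a stratified Cox hazard ratio. Three kinds of non-fatal component matter here.

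- **Ascites:** "Time to uncontrolled ascites (diuretic resistant ascites requiring therapeutic paracentesis at a frequency of at least twice in a month"). It is a bullet of its own with no further condition. Section 6.3 has the same definition, also on its own: "Uncontrolled ascites (diuretic resistant ascites requiring therapeutic paracentesis at a frequency of at least twice in a month").
- **Variceal bleed, encephalopathy, bacterial peritonitis:** "Hospitalization (as defined by a stay of 24 hours or greater) for new onset or recurrence of" these events.
- **MELD of 15 or more:** counted only "for patients with MELD ≤ 12 at baseline".

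Table 7 in section 11, and the Criteria for Evaluation table in the synopsis, word it differently: "hospitalization for new onset or recurrence of: variceal bleed, hepatic encephalopathy, spontaneous bacterial peritonitis, uncontrolled ascites, and HCC".

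On entry, section 8.2 accepts clinical signs "consistent with cirrhosis including: gastroesophageal varices, ascites, radiological evidence of cirrhosis" and admits Child-Pugh scores up to 12 ("Severe: CP-C (Scores 10 to 12"). None of the 16 exclusions in section 8.3 names ascites.

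**The concern.** Needing paracentesis at least twice a month is a continuing state. A patient already in that state on Day 1 meets the wording of 15.6 about a month later in either arm, whatever the treatment does. The MELD component shows that the plan recognises this problem, since patients already near the threshold are taken out of it. The ascites component has no such guard in 15.6 or 6.3.

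Events of this kind describe status at entry. They would cluster at the start of the curves in both arms and move the hazard ratio towards 1, hiding harm as readily as benefit. In the first-event composite they would also pre-empt the patient's later death, transplant or bleed. The events have a use beyond this trial: section 5.4.1 intends them for a combined evaluation with Study 747-302, and section 5.4.4 partly justifies the placebo arm by the high event rate expected.

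**Working it through.** **Can such a patient be enrolled?** In Table 12 (section 14.1.1), moderate-severe ascites scores 3. With the other four items at 1 point each the total is 3 + 4 × 1 = 7, which is Child-Pugh B and satisfies inclusion criterion 3. Exclusion 6 removes fluctuating or rapidly deteriorating hepatic function in the investigator's opinion, and exclusion 7 removes hepatorenal or hepatopulmonary syndrome. They may catch some of these patients. Neither removes stable diuretic-resistant ascites as such.

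**Do the passages agree?**

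| Place | New onset or recurrence required? | Hospital stay required? |
|---|---|---|
| 6.3, 15.6 | No | No |
| Table 7, synopsis Criteria for Evaluation | Yes, as punctuated | Yes, as punctuated |

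The Table 7 list also sweeps in HCC, which 15.6 analyses separately, so the list may be loose drafting. Either way the two definitions differ.

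**Size.** The Protocol states no event rate, hazard ratio or prevalence for these events, so there is no figure of its own to reproduce. Everything below is assumed except 25 patients per arm and 48 weeks.

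- Prevalence p is equal in both arms. A prevalent case has its event uniformly over the first 4.3 weeks. All event times are otherwise exponential.
- Placebo risk 30%: λ0 = −ln(0.70)/48 = 0.00743 per week. With a true hazard ratio of 0.50, the OCA risk is 1 − 0.70^0.5 = 0.163.
- Proportion event-free in arm j: S_j(t) = e^(−λ_j t) × [(1 − p) + p × max(0, 1 − t/4.3)], with event density f_j = −S_j′.
- The value b to which the Cox log hazard ratio tends solves ∫ [f1 − (f0 + f1) × S1e^b/(S1e^b + S0)] dt = 0 over 0 to 48 weeks.

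| Assumed true HR, placebo risk | p = 0% | 5% | 10% | 20% |
|---|---|---|---|---|
| 0.50, 30% (composite) | 0.500 | 0.571 | 0.629 | 0.718 |
| 0.50, 45% (composite) | 0.500 | 0.548 | 0.591 | 0.666 |
| 1.50, 30% (composite, harm) | 1.500 | 1.425 | 1.364 | 1.272 |
| 0.60, 10% (ascites component alone) | 0.600 | 0.736 | 0.809 | 0.884 |

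Share of composite events that are prevalent cases (true HR 0.50, placebo risk 30%): 2p / [2p + (1 − p)(0.30 + 0.163)].

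- 5%: 0.10/0.540 = 18.5%
- 10%: 0.20/0.617 = 32%
- 20%: 0.40/0.771 = 52%

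**Chance imbalance.** With 50 patients split 25 and 25, five prevalent cases (10%) differ between arms by three or more with probability 35% (hypergeometric). With ten cases (20%) the probability is 29%. So in one small trial the error can also fall in either direction.

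**The case against.** **Table 7 already supplies the condition.** As punctuated, it does, and it would be wrong to infer that the Protocol nowhere attaches new onset to ascites. But 15.6 is where the analysis is defined, and 6.3 agrees with 15.6. This is a conflict to settle and does not answer the point.

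**The adjudication charter or SAP may handle baseline status.** Sections 14.2.3 and 15.9 send events to blinded adjudication, only those after first dose qualify, and 15.6 leaves further detail to the SAP. A committee might decline to count an unchanged baseline state, so the text does not show that prevalent cases will certainly be counted. It also states no rule that stops this: a paracentesis after first dose in a prevalent case satisfies 15.6 as written. The event definition is fixed in the Protocol, with baseline conditions given for its neighbours.

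**Prevalence is unknown.** This stands. Ascites as evidence of cirrhosis, or a moderate-severe Child-Pugh item, does not mean paracentesis twice a month. A reader might infer that the hazard ratio will be diluted. The documents support only that it would be if such patients are enrolled and counted.

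**Later events are lost.** A reader might infer this too. Later events drop out of the first-event composite only, because 15.6 also analyses each event separately and still counts them there.

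**The endpoint is additional and imprecise.** This stands as well. No efficacy hypothesis is tested. With 25 per arm, 30% placebo risk and HR 0.50, expected events are 25 × 0.30 = 7.5 and 25 × 0.163 = 4.1. The standard error of the log hazard ratio is about √(1/7.5 + 1/4.1) = 0.61, an approximate 95% range of 0.15 to 1.7. A shift from 0.50 to 0.57 or 0.63 is small beside that. This limits the priority but does not make the definition right.

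**Conclusion.** The concern holds in conditional form. Sections 6.3 and 15.6 define uncontrolled ascites as a state with no new-onset or baseline condition, no exclusion keeps out patients already in that state, and Table 7 and the synopsis table say something different.

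If such patients are enrolled and counted under 15.6 as written, an assumed hazard ratio of 0.50 would tend to about 0.57, 0.63 or 0.72 at 5%, 10% or 20% prevalence with 30% placebo risk, and to about 0.55, 0.59 or 0.67 with 45%. A harmful ratio of 1.5 (30% placebo risk) would shrink to about 1.43, 1.36 or 1.27. The ascites component alone is affected more. These figures rest on assumed rates, equal prevalence in the arms and prevalent events within the first month. At 0% prevalence the effect is nil. Priority is moderate.

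**What to change.** 1. In 15.6 and 6.3, count uncontrolled ascites only in patients who did not meet its definition before first dose.
2. Keep patients who did meet it in the composite, at risk for all other components.
3. Record baseline status by a specific question in the Screening or Day 1 history. For patients already enrolled, take it from medical history and source records. The existing procedure record is not enough alone: on Day 1 it covers only the time since Screening, 14 to 28 days earlier, and the medical history does not ask for paracentesis frequency.
4. List baseline uncontrolled ascites by arm.
5. Align Table 7 and the synopsis Criteria for Evaluation with 15.6, including whether a hospital stay is required.

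The cost is a sentence in each of two sections, one history item, one listing and two table edits. The downside is small: a few patients are not at risk for one component. No treatment or visit changes.

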5.4.4. Rationale for Control Group

The use of a randomized placebo control group added to established standard of care provides the best scientific evidence of efficacy and safety. The use of a placebo control provides a concurrent comparator group, accounting for not only a placebo effect but continued standard of care. The use of a placebo control is critical to assess the safety and tolerability of OCA but also as a comparator for the high rate of clinical events which are expected in this advanced population.

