9.4. Randomization and Blinding

9.4.1. Methods of Assigning Patients to Treatment Groups

This study will be conducted in a double-blind, placebo-controlled manner. Enrolled patients who meet all eligibility requirements will be randomized in a 1:1 ratio to 1 of 2 treatment groups: placebo or OCA based on a predefined randomization code (generated by Sponsor or designee) using an interactive web response system (IWRS), which the Sponsor intends will serve as a computer-based patient registration system at Screening and Day 1.

Randomization will be stratified by CP class (CP-B or CP-C). Baseline MELD scores will be monitored on an ongoing basis to ensure adequate distribution of MELD scores. The IWRS will

serve as the investigational product inventory and management system and may be integrated with the study database.

The Investigator or designee will be required to register the patient in the IWRS and may be prompted to provide patient data necessary to properly randomize and allocate the patient to treatment. A randomization number will be assigned and investigational product (OCA or placebo) dispensing information will be provided (eg, bottle numbers allocated) while maintaining the study blind.

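### Section 15.6 uses Kaplan-Meier for each single clinical event and HCC although death precludes them, so read as event probabilities the curves and quartiles run too high, slightly at 48 weeks and more by 3 years

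*Protocol*

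**What the plan says.** Protocol section 15.6 lists all-cause death, liver-related death, liver transplant, MELD of 15 or more (in patients starting at 12 or below), hospitalization for variceal bleed, encephalopathy or spontaneous bacterial peritonitis, and uncontrolled ascites. For the first occurrence of any of these it prescribes:

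- a log-rank test stratified by the randomization factor;
- KM estimation: "KM estimates of the distribution of the time-to-event will be tabulated and graphed by treatment group", with the 25th, 50th and 75th percentiles;
- counts: "The number and percent of patients censored and with events will be presented";
- a hazard ratio: "The hazard ratio and 2-sided 95% CI will be estimated based on a Cox regression model stratified by randomization strata".

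It then turns to the single events: "In addition, the incidence and time to each of the above clinical events, and the incidence and time to occurrence of hepatocellular carcinoma (HCC"). The method for all of these is fixed in the same sentence, which ends by saying that they "will be summarized by treatment group using the same methods as defined above". The synopsis repeats this. HCC is not in the composite list, so this is its only analysis.

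Neither place names a competing-risk method or says how a death before another event is handled. Section 5.4.4 speaks of "the high rate of clinical events which are expected in this advanced population". Section 7.1.3 sets at least 48 weeks of double-blind treatment, continuing until all patients finish and the database is locked, at about 3 years.

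**The concern.** A patient who dies cannot later bleed, develop HCC or receive a transplant, and a death from another cause rules out a liver-related death. A KM curve for such an event has to censor the death. It then behaves as if the dead patient had the same future risk as those still followed. The curve therefore estimates how often the event would occur if nobody died, which is not the proportion of patients who will have it.

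The excess grows with the competing rate and with time. It can also differ between arms: if more patients die in one arm, its KM curve is inflated more. The study tests no formal hypothesis, so these descriptive curves and quartiles are the product of the analysis. Section 5.4.1 also foresees evaluating the clinical outcomes together with those of Study 747-302.

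**Working it through.** The protocol states no event rate, event count or hazard ratio for the clinical events, so there is no figure of its own to reproduce.

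**Inputs**
- From the protocol: times of 48 weeks (48/52 = 0.923 year) and about 3 years (section 7.1.3); about 50 patients randomized 1:1, so about 25 per arm (section 15.2).
- Assumed: constant cause-specific rates per year of λ1 = 0.10 to 0.20 for the single event and λ2 = 0.05 to 0.50 for the competing event.

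**Formulas**
- What KM estimates when the competing event is censored: 1-KM = 1 - exp(-λ1·t).
- Actual probability of the event: CIF = λ1/(λ1+λ2) × [1 - exp(-(λ1+λ2)·t)].

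**One case in full** (λ1 = λ2 = 0.20)
- 48 weeks: 1 - exp(-0.185) = 16.9%, against 0.5 × [1 - exp(-0.369)] = 15.4%.
- 2 years: 1 - exp(-0.4) = 33.0%, against 0.5 × [1 - exp(-0.8)] = 27.5%.
- 3 years: 1 - exp(-0.6) = 45.1%, against 0.5 × [1 - exp(-1.2)] = 34.9%.

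**Range over λ2 = 0.05 to 0.50** (excess taken from unrounded values)

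| Time | λ1 | 1-KM | CIF | Excess (points) |
|---|---|---|---|---|
| 48 weeks | 0.10 | 8.8% | 8.6% to 7.1% | 0.2 to 1.7 |
| 48 weeks | 0.20 | 16.9% | 16.5% to 13.6% | 0.4 to 3.3 |
| 3 years | 0.10 | 25.9% | 24.2% to 13.9% | 1.8 to 12.0 |
| 3 years | 0.20 | 45.1% | 42.2% to 25.1% | 2.9 to 20.0 |

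As a ratio, 1-KM is too high by a factor of 1.02 to 1.24 at 48 weeks and 1.07 to 1.86 at 3 years.

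**Quartiles** (λ1 = 0.15, λ2 = 0.30)
- The KM 25th percentile is ln(4/3)/0.15 = 1.9 years. The CIF reaches 25% when exp(-0.45·t) = 0.25, that is at ln(4)/0.45 = 3.1 years.
- KM gives a median of ln(2)/0.15 = 4.6 years. The CIF never exceeds 0.15/0.45 = 33%, so it has no median.

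**Unequal competing rates** (λ1 = 0.20 in both arms, 3 years)
- With λ2 = 0.10 in one arm and 0.30 in the other, both KM curves give 45.1%. The actual probabilities are 39.6% and 31.1%, a difference of 8.5 points that the KM display does not show.

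**Not affected**
- All-cause death has no competing event.
- The composite already counts death and transplant as events.
- The crude number and percent with events do not use KM.
- A Cox model that censors at the competing event estimates a valid cause-specific hazard ratio.

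**The case against.** **The SAP may settle it.** Section 15.6 leaves full details to the SAP, which is not at hand, and competing-event rules are normal SAP content. That would answer a complaint about silence. Here, though, the protocol itself names the estimator, so deferring details does not remove it.

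**Incidence is also reported as a crude percent.** True, and that percent is not inflated in this way. With follow-up running from 48 weeks to about 3 years it is not a risk at any fixed time, and it does not correct the curves and quartiles.

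**The size is small against the noise.** This largely stands at 48 weeks. With 25 per arm, a 30% estimate has a 95% half-width of about 1.96 × √(0.3 × 0.7/25) = 18 points even without censoring. The large figures belong to 3 years, which later entrants will not reach. Still, this is a systematic error that can be avoided at almost no cost.

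**Stronger readings the documents do not support**
- *The hazard ratios are distorted by competing events.* They are not; they only need the cause-specific label.
- *Leaving baseline MELD out of the Cox model biases it.* MELD is indeed only watched: "Baseline MELD scores will be monitored on an ongoing basis to ensure adequate distribution of MELD scores". But "Randomization will be stratified by CP class (CP-B or CP-C"), and the Cox model uses the same strata, so randomization protects the comparison. In simulation (assumed baseline rate 0.2 per year over 3 years, log-hazard 0.5 to 1.0 per SD of MELD, n = 4000), a true hazard ratio of 1.0 came out at 0.99 to 1.00 without MELD. A conditional 0.5 came out at 0.52 to 0.57, which is non-collapsibility, a different and conservative estimand. At n = 50 the SD of the log hazard ratio was 0.43 to 0.50 without MELD and 0.44 to 0.53 with it, so precision did not improve. Chance imbalance is random error of the kind the confidence interval covers.
- *Transplant is censored.* No rule says so. Table 4 in section 7.4.3 stops treatment after transplant but keeps the patient on scheduled visits.

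**Conclusion.** The point holds for the KM curves and quartiles of each single event other than all-cause death, and of HCC. Read as event probabilities, they are too high wherever deaths occur first. Under the assumed rates the excess is at most about 3 points at 48 weeks and between about 2 and 20 points at 3 years. The direction does not depend on the assumed rates; the size does, and the protocol offers none to replace them. The calculation also assumes constant rates. The severity is modest: these are additional objectives without formal testing, and the composite, all-cause death, crude counts and cause-specific hazard ratios stand as planned.

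**What to change.** In section 15.6, the matching synopsis text and the SAP:

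- For each single event other than all-cause death, and for HCC, replace KM with Aalen-Johansen cumulative incidence by arm. Treat death as a competing event (for liver-related death, death from other causes).
- State for each event whether transplant precludes or materially alters it. If so, treat it as competing; if not, keep the patient at risk.
- Report cumulative incidence with 95% intervals at 48 weeks and at later times with enough patients at risk. Give a percentile only where the curve reaches it.
- Label the single-event Cox result a cause-specific hazard ratio.
- Keep KM for all-cause death and for the any-event composite.

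A MELD-adjusted Cox model is at most an optional supportive analysis and is not needed for this point.

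The cost is wording and a different estimator in the programs. No new data are needed: deaths and transplants are already endpoints, and section 15.9 has all deaths and suspected liver-related outcomes adjudicated.
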